### 16.2 Primary Hypothesis

#### *MADRS*

The primary study hypothesis is that treatment with NRX-101 is superior to lurasidone in improving symptoms of depression as measured by the MADRS over 6 weeks of treatment. The primary study hypothesis is that treatment with NRX-101 is superior to lurasidone in improving symptoms of depression as measured by the MADRS over 6 weeks of treatment. The null hypothesis for the primary endpoint is the mean change from baseline of MADRS-10 for NRX-101 is the same as lurasidone. Baseline is defined as MADRS-10 score at study entry.

The null hypothesis is no difference in the mean change in the MADRS-10 score from baseline to Day 42/exit between both treatment groups, while the alternative hypothesis is that there is a larger mean improvement in the NRX-101 group than the lurasidone group. The study is to have 80% power to detect a 0.66 effect size post-randomization for a two-sided test with 5% Type 1 error using mixed model repeated measures (MMRM).

### 16.3 Secondary Hypotheses

The secondary hypothesis are that:

- treatment with NRX-101 is superior to lurasidone in improving symptoms of suicidality as measured by the CGI-SS over 6 weeks of treatment. The null hypothesis is the mean change from baseline of CGI-SS for NRX-101 is greater than or equal to the mean change from baseline of CGI-SS for lurasidone while the alternative hypothesis is that the mean change from baseline of CGI-SS is less than the mean change from baseline of CGI-SS for lurasidone (improvement). Baseline is defined as CGI-SS score at this study entry.
- that NRX-101 is superior to lurasidone in time to treatment failure as defined as: study discontinuation due to Adverse Events; psychiatric hospitalization; or requiring a change in antidepressant treatment. Time to treatment failure may be ascertained as the treating physician's determination of a study discontinuation due to lack of efficacy; withdrawal due to a treatment related adverse event a psychiatric hospitalization; or the patient requiring any change in their baseline antidepressant, mood stabilizer, or antipsychotic medication. Titration or change in timing of administration of study medication will not be considered a failure of therapy. Lack of efficacy is defined as the need to implement a new treatment plan or an increase in suicidal ideation (a score of 4 or 5 on the C-SSRS, emergent suicidality requiring hospitalization), or increase in depressive symptoms (a score increase of  $\geq 5$  for two consecutive visits on the MADRS total score). The need to implement a new

treatment plan includes the addition of new antidepressant medication or somatic treatment (e.g. ECT or rTMS treatment) or an escalation of care such as hospitalization (i.e. moving the patient from outpatient care to initiating inpatient, partial or day hospitalization). Time to failure will be assessed using a Kaplan-Meier lifetable. The formal hypothesis test will be to detect a 0.421 hazard ratio (HR) with 80% power for a two-sided test using a proportional hazard model; a 0.545 hazard ratio reaches two-sided  $p=0.05$ .

## 17. ENDPOINTS

### 17.1 Efficacy

#### 17.1.1 Primary Efficacy Endpoint

The primary efficacy endpoint is the change from baseline in the total MADRS score as measured by psychometric raters assessed over 42 days post randomization by mixed-model repeated measures analysis.

The primary endpoint will be based on adjudicated results. All rating sessions for MADRS-10 and C-SSRS will be recorded as audio files and reviewed by central master-raters with  $> 25$  years of experience. Any MADRS-10 total score that differs by more than three points from the master-rater score will be deemed non-congruent. All non-congruent subject-visits from any site with  $>10\%$  non-congruent scores will be sent to an independent adjudicator, previously determined to have  $>90\%$  concordance with study master raters on standardized training data. In the event of adjudication as above, the independent outside rater score shall be considered as the subject-visit primary study endpoint.

#### 17.1.2 Secondary Efficacy Endpoints

The secondary efficacy endpoints are:

- Change from baseline in CGI-SS score as measured by treating prescriber assessed over 42 days post randomization by mixed-model repeated measures analysis.
- **Time to Treatment Failure (TTF):** A Kaplan-Meier lifetable will be constructed for the time to failure of therapy. Failure of therapy will be defined as the treating physician's determination of a study discontinuation due to lack of efficacy; withdrawal due to a treatment related adverse event a psychiatric hospitalization; or the patient requiring any change in their baseline antidepressant, mood stabilizer, or antipsychotic medication. Titration or change in timing of administration of study medication will not be considered a failure of therapy.

The additional secondary efficacy endpoints are:

- Change from baseline in each item of the Suicide Ideation and Behavior Assessment Tool (SIBAT) Module 7 (clinical global impressions of frequency of suicidal thinking, severity of suicidality, and imminent and long-term risks).
- Change from baseline to endpoint in Suicidal Thoughts on the MADRS (MADRS item 10)

- Change from baseline to Day 14 in total MADRS score
- Change from baseline for each MADRS-10 factor at each post-baseline evaluation including exit.
- Change from baseline for the three MADRS-10 factors defined by Borenstein at each post-baseline evaluation including exit.
- Change from baseline to endpoint (Day 42/exit) in MADRS total score in the subgroup of participants who were recently (within 2-weeks before enrollment) placed on approved medications for bipolar depression as well as the 5-HT2A subset.

### 17.1.3 Additional Efficacy Endpoints

The following other efficacy endpoints will be explored:

- **Remission from suicidality:** A Kaplan-Meier lifetable will be constructed for the remission duration from response onset where remission is defined as reaching CSSR-S  $\leq 2$  and remaining through the study. Remission rate is defined as percent remaining in remission.

Collectively, symptom improvement will be evaluated by assessing changes in the secondary outcome measures within and between treatment groups for each of the following at the times specified on the Schedule of Study Activities:

- Montgomery Asberg Depression Rating Scale (MADRS) ([Montgomery, Åsberg 1979](#))
- Clinical Global Impression of Severity of Suicidality Scale (CGI-SS)
- Concise Health Risk Tracking – Self Report (CHRT-SR) and Clinician Rating (CHRT-C) scales ([Trivedi et al., 2011](#))
- Brief Psychiatric Rating Scale (BPRS) ([Overall and Gorham, 1962](#)).

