16.8.6 Other Time to Event Efficacy Endpoints

Other time-to-event outcomes (all-cause discontinuation, and remission duration) further characterize this multi-component disorder. Time to event is a more sensitive measure than an assessment at a fixed time. Time to such events will be displayed using a Kaplan-Meier lifetable, with the treatment groups compared using two-sided unstratified log rank tests (secondary) and a proportional hazard model (primary) to include the above cited baseline covariates.

Treatment Failure will be centrally judged blind in real time by the study physician using baseline measures of depression and suicidality as a guide. Treatment failure is defined above.

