Endpoint(s):	
Primary Efficacy Endpoint:
 
 
• Change from baseline over 42 days in MADRS total score.
 
 
Secondary Efficacy Endpoints:
 
 
• Change from baseline over 42 days in CGI-SS.
 
• Time to treatment failure (TTF).
 
• Change from baseline in Suicidal Thoughts on the MADRS (MADRS item 10).
 
• Change from baseline to Day 14 in MADRS total score.
 
• Change from baseline for each MADRS-10 factor at each post-baseline evaluation including exit.
 
• Change from baseline for the three MADRS-10 factors defined by Borenstein at each post-baseline evaluation including exit.
 
• Change from baseline in each item of the Suicide Ideation and Behavior Assessment Tool (SIBAT) Module 7 (clinical global impressions of frequency of suicidal thinking, severity of suicidality, and imminent and long-term risks).
 
• Change from baseline to endpoint (Day 42/exit) in MADRS total score in the subgroup of participants who were recently (within 2-weeks of enrollment) on approved medications for bipolar depression as well as the 5-HT2A subset.
 
• Percent in remission from suicidality at Day 42/exit (exploratory endpoint).
 

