## 7.4 Safety Objectives

- To test the hypothesis that treatment with NRX-101 is superior to lurasidone (a standard of care drug) in reducing suicidality in depressed bipolar participants with SSIB, as measured by the Columbia Suicide Severity Rating Scale (C-SSRS)
- To test the hypothesis that remission from suicidality, measured as Week 6 percent with C-SSRS  $\leq 3$  will be superior for NRX-101 relative to lurasidone

[figure not shown]
- To test the hypothesis that participants treated with NRX-101 are less likely to suffer from akathisia than those treated with lurasidone as measured by the Barnes Akathisia Rating Scale (BARS)
- To test the hypothesis that fewer participants treated with NRX-101 will be discontinued for lack of efficacy or exacerbation of suicidality than participants treated with lurasidone.

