## 20. STATISTICAL METHODOLOGY

### 20.1 General Methodology

The Mixed-Effect Model Repeated Measure (MMRM) will be the primary analysis for the primary efficacy endpoint (MADRS change from baseline); an unpaired t-test will be a secondary analysis. The proportional hazard model (PHREG) will be the primary analysis for time to event endpoints (time to remission, time to discontinuation); the unstratified log rank test will be a secondary analysis. The MMRM and PHREG models will all include treatment and the following four baseline covariates:

- sex
- mood stabilizer use
- anti-psychotic use
- evidence of suicide event in their lifetime.

All primary analyses will be in the mITT population as primary and repeated in the Per Protocol population if >5 percent are excluded.

All of the instruments used to measure SSIB or depression constitute serial continuous and ordinal outcomes that will be analyzed using MMRM with LOCF to account for missing data and early discontinuations. The models will include treatment group, study visit, the interaction between study visit and treatment group, the baseline level of the variable being analyzed, and the above four pre-defined baseline stratification factors as fixed effects. The primary endpoint change from baseline MADRS-10 will be analyzed using the MMRM model which will include baseline MADRS; treatment group; study visit; study visit\*treatment; sex, mood stabilizer use, anti-psychotic use, and evidence of suicide event in their lifetime as defined above. An unstructured error structure will be assumed.

SAS PROC MIXED will be used for continuous endpoints.

In addition, supportive analyses will be performed using multiple imputation which will be performed to address any missing data. The method of Little and Rubin will be used. The presentation of the results for the primary efficacy endpoints using the ITT population will be based on the observed data with multiple imputation for missing endpoint data using SAS PROC MI. Missing data will be imputed using MCMC imputation under the assumption of a missing at random using the mITT population. The SAS® procedure PROC MI will be used for the MCMC imputation of 25 complete data sets.

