### 20.2 Other Time to Event Efficacy Endpoints

Other time-to-event outcomes (all-cause discontinuation, and time to remission) further characterize this multi-component disorder. Time to event is a more sensitive measure than an assessment at a fixed time. Time to such events will be displayed using a Kaplan-Meier lifetable,

with the treatment groups compared using two-sided unstratified log rank tests (secondary) and a proportional hazard model (primary) to include the above cited baseline covariates.

Treatment Failure will be centrally judged blind in real time by the study physician using baseline measures of depression and suicidality as a guide. Treatment failure is defined above.

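### SAP 17.1.3 builds lasting to study end into its definition of suicidality remission, so its remission-duration curve, read literally, can have no loss events; it should be reconciled with SAP 20.1 and 20.2

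*SAP*

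**What the plan says.** SAP 17.1.3 lists remission from suicidality among the endpoints to be explored: "A Kaplan-Meier lifetable will be constructed for the remission duration from response onset where remission is defined as reaching CSSR-S" of 2 or less, "and remaining through the study. Remission rate is defined as percent remaining in remission". Protocol 16.4.3 has the same wording, so this is not a slip made in drafting the SAP.

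The methods sections do not agree on the variable. Protocol 16.8.6 says: "Other time-to-event outcomes (all-cause discontinuation, and remission duration) further characterize this multi-component disorder". SAP 20.2 says: "Other time-to-event outcomes (all-cause discontinuation, and time to remission) further characterize this multi-component disorder". SAP 20.1 likewise makes the proportional hazards model the "primary analysis for time to event endpoints (time to remission, time to discontinuation"). SAP 13 says that the SAP governs where it differs from the protocol.

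The SAP also plans remission at a fixed time. Its synopsis lists "Percent in remission from suicidality at Day 42/exit (exploratory endpoint"), and SAP 7.4 has the objective "To test the hypothesis that remission from suicidality, measured as Week 6 percent with C-SSRS" of 3 or less.

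**The concern.** The event on a duration-of-remission curve is loss of remission. Under SAP 17.1.3 that event also cancels membership of the group being followed: anyone who relapses is reclassified as never having remitted. The curve therefore contains only patients chosen because they did not relapse. That makes it uninformative about durability. It also means the comparison is not between randomized groups, because patients enter it on the strength of their later outcome.

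At stake is how one suicidality result would be read, in a trial that enrols patients for suicidal ideation. A tabulated figure of 100% remaining in remission could be taken as evidence of durable benefit when the definition alone produces it.

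**Working it through.** The documents give no expected number of remitters, loss events or power for this endpoint, so there is no figure of theirs to reproduce. The check is one of logic.

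**Inputs.** The cut-off is C-SSRS of 2 or less (SAP 17.1.3). In SAP Table 1 the post-baseline C-SSRS ratings are on Days 7, 14, 28 and 42, with none at Day 70. That gives four ratings per completer.

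**Step 1: the estimator.** Kaplan-Meier is S(t) = Π(1 − d/n), taken over event times, where d is the number losing remission and n the number at risk. The definition forces d = 0 throughout, so S(t) = 1 for every t. A log-rank test or proportional hazards model for duration, as in protocol 16.8.6, would have no events to work with.

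**Step 2: enumeration.** Code each rating R (2 or less) or N (above 2), and let a patient leave after any visit. The number of paths is 2 + 4 + 8 + 16 = 30.

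- *As written.* A path qualifies if it ends in an unbroken run of R, counting early leavers who exit in remission. That is 1 + 2 + 4 + 8 = 15 paths, and loss events number 0. Among the 16 completer paths, 8 qualify, again with 0 losses.
- *Durability condition removed.* Entry is at the first R and the event is a later N. Paths entering: 30 − 4 = 26. Paths with no loss have the form N…NR…R, and there are 1 + 2 + 3 + 4 = 10 of them. Paths with a loss: 26 − 10 = 16. Among completers, 15 enter and 15 − 4 = 11 contain a loss.

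These count possible paths and are not probabilities. They show that the condition alone removes every event.

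**Step 3: an invented example.** Assume 37 mITT patients per arm, no early leavers, 20 against 10 ever reaching the cut-off, and 5 in each arm then rising above it and staying there.

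| Quantity | Arm A | Arm B |
|---|---|---|
| Percent remaining, SAP 17.1.3 read literally | 15/15 = 100% | 5/5 = 100% |
| Sustained remission over all patients | 15/37 = 40.5% | 5/37 = 13.5% |
| Loss after first reaching the cut-off | 5/20 = 25% | 5/10 = 50% |

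**Step 4: comparing the sections.** SAP 17.1.3 and protocol 16.4.3 and 16.8.6 concern how long remission lasts. SAP 20.1 and 20.2 concern how long it takes to begin, which can be estimated because remission itself is the event. SAP 20.1 and 20.2 do not say which remission they mean. Since time to remission stands where the protocol had remission duration, suicidality remission is the natural reading.

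**Step 5: loose ends.** Response onset, which starts the clock, is not defined. A patient first at the cut-off on Day 42 counts as sustained with no follow-up at all. The handling of patients who leave early while in remission is not stated.

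**The case against.** The strongest reply is that the literal reading is not the only one. Speaking of a duration and of a percentage remaining presupposes that remission can be lost. On a looser reading everyone who reaches 2 or less enters at response onset, a later rise is the event, and those who last to the end form the numerator. Equally, if the denominator were all mITT patients, the percentage would be the sustained-remission proportion, which is informative. Both points stand to this extent: the 100% figure depends on taking the definition literally with remitters as the denominator. But the looser reading has to set aside the durability condition and needs a definition of response that the documents lack, and SAP 17.1.3 does not state an all-mITT denominator.

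It can also be said that the SAP has largely moved on. Its methods sections already replace remission duration with time to remission, and 17.1.3 looks like text carried over from the protocol. That is mitigation, and it makes the repair simple, but the endpoint section still says something else.

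A reader might go further and infer that the plan cannot distinguish the arms on remission from suicidality. The documents do not support that. Besides time to remission, the SAP plans the Day 42/exit percentage, the Week 6 percentage at 3 or less, and a between-arm Jonckheere-Terpstra comparison of C-SSRS (SAP 20.5). In the example above, the 15/37 against 5/37 contrast is what the Day 42/exit endpoint would report at the same cut-off. Nor would 100% in both arms favour NRX-101.

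**Conclusion.** The point holds as a circular definition in SAP 17.1.3 that makes one exploratory analysis uninformative and leaves it inconsistent with SAP 20.1 and 20.2. The absence of loss events follows from the wording and needs no numerical assumption. The 100% rate follows if remitters are the denominator and the arm has at least one remitter. The example counts are invented and estimate nothing about this trial.

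The consequence is limited. The endpoint lies outside the testing hierarchy in SAP 18.3 (MADRS, then CGI-SS, then time to treatment failure), so no primary or hierarchical conclusion is touched. The change is still worth making, because the text is a stated rule with an automatic answer and not merely a missing detail. The fixed-time endpoints do not fully stand in for it either: the synopsis gives the Day 42/exit percentage no cut-off of its own, and SAP 7.4 uses 3 or less where 17.1.3 uses 2 or less.

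**What to change.** Before database lock, reword SAP 17.1.3 as follows.

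1. **Between-arm analysis.** Use time from randomization to first reaching the cut-off, in all mITT patients, by the methods already in SAP 20.1 and 20.2. State there that suicidality remission is meant. This variable claims nothing about durability, so a patient first at the cut-off on Day 42 causes no difficulty.
2. **Duration, if kept.** Remove the condition that remission last through the study. Start the clock at the first visit at or below the cut-off, and make the event the first later visit above it. Label the curve descriptive, because it is limited to responders. A patient who first qualifies on Day 42 then contributes no follow-up.
3. **Remission rate.** State that the denominator is all mITT patients, use one cut-off throughout, and prespecify how early leavers are counted, consistently with the Day 42/exit endpoint. Counting them as not remitted is one option. What matters is that the rule is fixed in advance.

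The cost is SAP wording only; the C-SSRS data are already collected. The reported remission rate will fall below the automatic 100%.

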### 17.1.4 Other Efficacy Endpoints

The following additional endpoints will be recorded and analyzed by treatment group:

- Dose per treatment group
- Suicide rates (attempted and completed)
- Time to all-cause study discontinuation (and reason for discontinuation) due to any reason such as withdrawal due to an adverse event, or patient or investigator decision to withdraw
- Rate of participants who achieve a resolution of suicide risk by Clinical Global Judgement of Suicide Risk [CGI-SS] 0 or 1) or by MADRS (suicidal ideation item #10 of 0 or 1)
- Percent in remission at Day 42/exit, defined as having achieved a MADRS score of  $\leq 10$  during the last two visits (14 days)
- Proportion of participants who are treated with new SSRIs or have increased SSRI dosages
- Proportion of participants who discontinue SSRIs or have reduced SSRI dosages

- Efficacy for each MADRS question as well as the three Borenstein factors.

### **17.1.5 Diagnostic Metric**

The following metrics will be evaluated at baseline:

- MINI 7.0.2

## **17.2 Safety Assessments**

- Change from baseline to endpoint (Day 42) in C-SSRS score
- Change from baseline to endpoint (Day 14) in C-SSRS score
- Mean change in BARS through Day 42 to assess akathisia
- Rates of discontinuation between the arms

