#### 12.1.3 Barnes Akathisia Scale (BARS)

The Barnes Akathisia (BARS) (Barnes, 1989) is a clinician-rated scale to assess drug-induced akathisia as absent, mild, moderate, or severe. It comprises items for rating the observable, restless movements which characterize the condition, the subjective awareness of restlessness, and any distress associated with the akathisia. In addition, there is an item for rating global severity. The timeframe for the scale is “at this time.”

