### **17.2.2 Other Safety Measures**

The timing and incidence of adverse findings will be compiled following planned surveillance of all study participants by a designated safety monitor.

Vital signs and ECGs will also be evaluated within and between study treatment groups. The overall ECG interpretation will be reported as normal or abnormal; if abnormal, then the percent clinically significant will be reported.

While symptom improvement will be evaluated by assessing changes in the secondary outcome measures (CHRT, MADRS, and CGI-SS), safety measures in the C-SSRS, PRISE, BPRS, and BARS (including the global severity rating) will be evaluated within and between study treatment

groups. The timeframe is for both lifetime and the past six months for the baseline Screening scale and since the last visit for the Since Last Visit scale.

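### SAP 17.2 measures akathisia as a mean BARS change and discontinuation without a cause, so no named test addresses the two safety hypotheses in 7.4 as worded

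*SAP*

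**What the plan says.** SAP 7.4 (and protocol 7.4) lists two hypotheses to be tested. On akathisia, judged by BARS: "participants treated with NRX-101 are less likely to suffer from akathisia than those treated with lurasidone". On discontinuation: "fewer participants treated with NRX-101 will be discontinued for lack of efficacy or exacerbation of suicidality than participants treated with lurasidone". Both are statements about how many participants are affected.

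The safety endpoints on the same subjects in SAP 17.2 are "Mean change in BARS through Day 42 to assess akathisia" and "Rates of discontinuation between the arms". The SAP synopsis, the protocol synopsis and protocol 16.5 list the same two items.

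Other sections bear on the point:

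- SAP 12.1.3 describes BARS as a scale to "assess drug-induced akathisia as absent, mild, moderate, or severe", and Table 1 schedules it at every visit from screening to Day 42.
- SAP 17.2.2 provides for a comparison of the arms: "BARS (including the global severity rating) will be evaluated within and between study treatment". It gives no case definition and no test.
- SAP 19.3 gives means an unpaired t-test at each time, with descriptive p-values, and gives ordinal and categorical variables frequencies.
- SAP 17.2.1 applies Fisher tests to adverse events by system class, and to preferred terms above 10% overall incidence.
- SAP 17.1.4, 20.2 and 20.4 analyse time to discontinuation from all causes. The reason is recorded.
- SAP 16.3 and 17.1.2 include discontinuation for lack of efficacy as one component of time to treatment failure (TTF).
- SAP 20.5 names tests for adverse events, laboratory values, C-SSRS, vital signs and ECG. It names none for BARS or for discontinuation by cause.

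**The concern.** A hypothesis about the number of participants with a condition needs an endpoint that counts participants. A mean change does not: it mixes how many are affected with how badly. Likewise, a hypothesis about two causes of discontinuation needs those causes separated from the rest. A rate with no cause named pools the hypothesised benefit with adverse-event and other exits, which may run in the opposite direction.

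Followed as written, the analysis could miss a true difference on either hypothesis, or show a difference that is not the one hypothesised. Akathisia matters here because protocol 6.3 gives blocking of lurasidone's anxiogenic effect as part of the rationale for the combination. If the BARS case threshold is not fixed in advance, it would also be open to choice after the data are seen.

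**Working it through.** **Inputs.** From the documents: 37 per arm (SAP 8), two-sided 5% level (SAP 19.3). The documents give no akathisia or discontinuation rates, so every rate or count below is an assumption, chosen to show what can happen.

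**The plan's own figure.** The only power statement behind the sample size is for MADRS: d = 8.85/13.4 = 0.66, and a two-sample t-test with 37 per arm then has 80.0% power. This agrees with SAP 18.2. No figure is stated for either safety hypothesis.

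**1. Mean versus proportion.** Take an illustrative global rating scored 0 to 5, with everyone at 0 on Day 1, so that the score equals the change.

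| Arm | Distribution | Mean | Proportion affected |
|---|---|---|---|
| A | 30% at 2, rest 0 | 0.30 × 2 = 0.60 | 30% |
| B | 15% at 4, rest 0 | 0.15 × 4 = 0.60 | 15% |

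The proportion affected halves and the means do not differ. Conversely, 20% at 2 against 20% at 4 gives means of 0.40 and 0.80 with equal proportions.

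**2. Pooled versus cause-specific discontinuation, example counts** (NRX-101 v lurasidone, two-sided Fisher exact, 37 per arm):

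| Discontinued for | Counts | p |
|---|---|---|
| Lack of efficacy or suicidality | 2 v 9 | 0.046 |
| Adverse events | 7 v 2 | 0.15 |
| Total | 9 v 11 | 0.79 |

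**3. The same over a range of assumed rates.** The chance of p ≤ 0.05 is the sum, over all pairs of counts that Fisher's test rejects, of Bin(a; 37, p1) × Bin(b; 37, p2).

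| Named causes | Other causes | Total | Named-cause test | Pooled test |
|---|---|---|---|---|
| 5% v 25% | 10% v 10% | 15% v 35% | 59% | 42% |
| 5% v 25% | 20% v 20% | 25% v 45% | 59% | 35% |
| 5% v 25% | 25% v 5% | 30% v 30% | 59% | 3% |
| 10% v 10% | 5% v 30% | 15% v 40% | 2% | 60% |

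The first three rows show the pooled rate diluting or hiding a named-cause difference. The last shows it producing a difference where the named causes do not differ.

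**4. Does another analysis close the gap?**

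- *BARS global-rating frequencies (17.2.2 with 19.3).* They describe participants by grade, but set no threshold for a case, give no rule for akathisia present at Day 1, and name no test.
- *Adverse-event term (17.2.1).* It rests on reported events, not BARS. The preferred term is tested only above 10% overall: 0.10 × 74 = 7.4, so at least 8 participants. Rates of 5% v 15% average exactly 10% and would not qualify.
- *Time to discontinuation (17.1.4, 20.2, 20.4).* All causes are pooled. Reasons are recorded, but no comparison by reason is named.
- *TTF (16.3, 17.1.2).* It pools lack of efficacy with adverse-event withdrawal, psychiatric hospitalization and change of medication.
- *The three Fisher measures in 20.4.* They are a new treatment plan, increased ideation and increased depressive symptoms. None is discontinuation.

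None is a between-arm test of either hypothesis as worded.

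**The case against.** The strongest reply is that the gap is narrow and the consequence low. Much of this stands.

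- A reader might infer that 17.2 specifies all-cause discontinuation. It does not; it names no cause. All-cause is the natural reading, but the SAP uses that term only for the time-to-event analysis. The pairing of objectives with endpoints is likewise inferred from subject matter.
- A reader might infer that BARS is analysed only as a mean. Sections 17.2.2 and 19.3 together support frequencies of the global rating per arm. What is missing is a case definition and a between-arm test.
- A reader might infer that akathisia carried in from a stopped antipsychotic, then resolving, cancels the treatment contrast. Randomization should balance such carry-over. With 6 resolved cases (−2 each) in both arms and 6 new ones (+2 each) on lurasidone only, the mean changes are −12/37 = −0.32 and 0, so the contrast survives. The documents also give no baseline akathisia rate. The case against the mean rests on step 1 of the working, not on carry-over.
- TTF covers part of the second hypothesis, since 16.3 counts increased suicidal ideation as lack of efficacy. It remains a composite.
- The count example is fragile: 2 v 8 instead of 2 v 9 gives p = 0.085. It shows what pooling can do, not what is likely.
- A cause-specific count has its own weakness. A participant who leaves for an adverse event can no longer leave for lack of efficacy, so more adverse-event exits could help to produce a low named-cause count. This is why the fix shows all exits together.
- Counting participants does not bring much power. For akathisia at 37 per arm, Fisher power is 16% for 5% v 15%, 36% for 5% v 20%, 59% for 5% v 25% and 78% for 5% v 30%.

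These points limit the size of the concern. They do not supply a test of either hypothesis.

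**Conclusion.** The mismatch is in the text. Two hypotheses about numbers of participants are matched with a mean and with a rate that names no cause, and the partial coverage elsewhere does not test either one. That the measures can diverge follows from their definitions; how far they would diverge in this trial is unknown, because every rate used above is an assumption.

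A reader might infer that the trial's main conclusions are at risk. The documents do not support that. The hierarchy in SAP 18.3 runs from MADRS to CGI-SS to time to treatment failure and includes neither safety hypothesis, and the sample size rests on MADRS alone. What is affected is the ability to support the trial's own statements on akathisia and on discontinuation for inefficacy or suicidality. The change should be made because it is cheap and fixes the case definition in advance.

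**What to change.** In SAP 17.2 and 20.5, add:

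1. The number and percent per arm with treatment-emergent akathisia by BARS, defined consistently with 17.2.1: global rating mild or worse post-baseline if absent at Day 1, or an increase in global rating over Day 1 if already present. Compare by two-sided Fisher exact test.
2. The number and percent per arm discontinued for lack of efficacy or exacerbation of suicidality, from the recorded reasons. Compare by two-sided Fisher exact test, and show beside discontinuation for adverse events, for other reasons and for all causes, so that competing exits are visible.

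Keep the mean BARS change and the overall discontinuation comparison. If the sponsor prefers the listed endpoints alone, the hypotheses in 7.4 should be reworded to match them.

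The cost is SAP wording, settled before unblinding, and two tables from data already collected. The downside is small: two more safety tests with modest power, reported without multiplicity control.
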